## STUDY SUMMARY

Study Title	GORE® CARDIOFORM ASD Occluder Clinical Study: A Study to evaluate safety and efficacy in the treatment of transcatheter closure of ostium secundum atrial septal defects (ASDs) – The Gore ASSURED Clinical Study
Protocol Number	ASD 15-04 - Revision 6 (06 Jan 2021)
IDE Number	G160218
Study Device	GORE® CARDIOFORM ASD Occluder
Sponsor	W. L. Gore & Associates, Inc. Medical Products Division [REDACTED] [contact] [REDACTED]
Study Design	Prospective, multicenter, single-arm comparison to performance goals derived from clinical study outcomes for devices indicated for ASD closure
Study Objective	Evaluate the safety and efficacy of the GORE® CARDIOFORM ASD Occluder in the percutaneous closure of ostium secundum atrial septal defects (ASDs)
Study Endpoints	
Primary Endpoints
 
Co-Primary Endpoint 1: 6-Month Closure Success is defined as a clinical residual defect status of occluded or clinically insignificant as determined by the Echo Core Lab at the 6-month evaluation among subjects with technical success.
 
Co-Primary Endpoint 2: Composite Clinical Success is evaluated at 6 months after index procedure among subjects with attempted study device closure and is defined as satisfying all of the following criteria:
 

1. Technical Success: Successful deployment and retention (at conclusion of index procedure) of a GORE® CARDIOFORM® ASD Occluder

2. Safety Success:

• Freedom from any Serious Adverse Event (SAE) related to the device or procedure (as adjudicated by the Independent Data Review Board (IDRB)) through 30 days post-procedure

• Freedom from device events (post-procedure embolization, device removal, or other device reintervention) from completion of the implant procedure through 6 months (180 days) post-procedure

3. Closure Success: A clinical residual defect status of occluded or clinically insignificant as determined by the Echocardiography Core Lab at the 6-month evaluation

 
Secondary Endpoints
 

• Technical Success

• Procedure Success

CONFIDENTIAL INFORMATION

	

• Long-term Composite Clinical Success

• Long-term Closure Success

• Safety Outcomes

• Clinically Significant New Arrhythmia

Subject Population	

• No age limitations

• Patients with ostium secundum ASD measuring 8-35 mm by stop-balloon sizing

• Inter-atrial shunting with evidence of right heart volume overload, demonstrating the need for septal defect closure

• Absence of concurrent cardiac conditions that could elevate morbidity/mortality beyond what is common for ASD

Number of Subjects	

• Training Cases: First 2 subjects per site

• Pivotal Phase: 125 subjects (non-training)

• Continued Access Phase: up to 535 subjects (non-training)

• Total Study Enrollment: up to 704 subjects

Number of Sites	Up to 22 sites in the U.S.
Coordination Principal Investigator	
[REDACTED]
 
[REDACTED]
 
[REDACTED]
 
National Principal Investigator, Pediatric
 
[REDACTED]
 
[REDACTED]
 
[REDACTED]
 
National Principal Investigator, Adult

Significant Inclusion Criteria	

• Patient has an ostium secundum ASD with evidence of left-to-right shunt and right ventricular volume overload.

• Patient has a defect size 8-35 mm as measured directly by stop-flow balloon sizing.

• Patient vasculature can accommodate the delivery system and procedural accessories.

• Patient can accommodate TEE or intracardiac echocardiography (ICE) probe for implant procedure.

• Patient is judged by the implanting physician to have adequate septal rims to retain the study device.

 
[REDACTED]
 
[REDACTED]

	

• [REDACTED]

Significant Exclusion Criteria	

• Patient has significant known pre-existing electrophysiologic or structural cardiovascular defect, or other comorbidities that could elevate morbidity or mortality beyond what is common for ASD or would require surgical treatment within three (3) years of device placement. Examples include, but are not limited to, large ventricular septal defect, hypoplastic left heart syndrome, coarctation, univentricular heart or tricuspid atresia, pulmonary hypertension, coronary artery disease, valvular or myocardial dysfunction, and other congenital heart disease requiring surgical repair.

• Patient has systemic or inherited conditions that would significantly increase risk of major morbidity and mortality during the term of the study. Examples include endocarditis, cancer, degenerative neuromuscular disorder, cardiomyopathy, and any condition expected to result in significant deterioration of health within three (3) years of the index procedure.

• Patient has anatomy where the size or position of the occluder would interfere with other intracardiac or intravascular structures, such as cardiac valves or pulmonary veins.

• Patient has active endocarditis, other infections producing bacteremia, or has known sepsis within one month of planned implantation, or any other infection that cannot be treated successfully prior to device placement.

• Patient has known intracardiac thrombi.

• Patient has an uncontrolled arrhythmia with evidence of arrhythmia

• Control failure within the past 90 days (e.g., supraventricular tachycardia while under rate control or atrial fibrillation while under rhythm control) or requires electrophysiology study or concomitant intervention with device placement.

• [REDACTED]

• Patient has a history of stroke resulting in a significant morbidity or disability.

• [REDACTED]

• Patient has elevated pulmonary vascular resistance (PVR) which in the opinion of the implanting physician precludes safe defect closure.

• Patient has multiple defects based on screening imaging and stop-flow balloon sizing that would require placement of more than one device.

Expected Time to Complete Enrollment	Pivotal Phase: Enrollment Completion: 12 months Continued Access: Enrollment Completion: 18-24 months

CONFIDENTIAL INFORMATION

Expected Time of each Study Subject to Complete the Study	36 months
Study Duration	Total Study Duration: 5.5 years
Schedule of Events	
Screening Assessments (within 6 months of procedure)
 

• Physical exam

• Electrocardiogram (ECG)

• Echocardiogram (TTE or TEE)

 
Pre-Study Procedure (within 90 days of procedure)
 

• Echocardiogram (TTE)

 
Procedure
 

• Physical exam

• Stop-flow balloon sizing of defect

• Echocardiogram (TEE, TTE or ICE)

• Fluoroscopy

 
Pre-Discharge
 

• Electrocardiogram (ECG)

• Echocardiogram (TTE)

 
30 days and 6 months:
 

• Physical exam

• Electrocardiogram (ECG)

• Echocardiogram (TTE)

• Fluoroscopy (6 months for all Subjects)

 
Long-term follow-up at 12 months and 36 months included:
 

• Physical exam

• Electrocardiogram (ECG)

• Echocardiogram (TTE)

• Fluoroscopy (36 months for all Subjects)

 
A telephone follow-up occurred at 24 months

Additional Information	Echocardiography Core Lab, Independent Data Review Board (IDRB)

CONFIDENTIAL INFORMATION

1.0 Introduction

This Statistical Analysis Plan (SAP) describes the statistical analyses planned to address the objectives of the ASSURED clinical trial. It details the analyses that will be performed to accomplish these objectives. This SAP defines variables and identifies methods and algorithms used to populate the tables, figures, and listings that are included in reports for this study.

2.0 Study Design

2.1 Primary Objective

The primary objective of this study is to evaluate the safety and efficacy of the GORE® CARDIOFORM ASD Occluder in the percutaneous closure of *ostium secundum* atrial septal defects (ASDs).

2.2 Design Summary

The Gore ASSURED Clinical Study is a prospective, multicenter, single-arm clinical study comparing outcomes for the GORE® CARDIOFORM ASD Occluder to performance goals derived from clinical investigation outcomes for devices indicated for ASD closure.

This clinical investigation will enroll up to 460 subjects (not including 2 training cases per site) from a protocol-specified maximum of 22¹ clinical investigational sites (referred to as “sites” in the remainder of this document) in the United States. Enrollment will occur in three phases: Pivotal (125 subjects, in addition to 2 training cases per site); Continued Access (up to 335 subjects); and Post-Approval (if required). Each phase will enroll sequentially.

All enrolled subjects with technical success will be followed through the 36-month follow-up; subjects with technical failure will be followed only through the 30-day follow-up. The analysis in support of pre-market approval submission will occur when the 125 pivotal (non-training) subjects have completed 6-month follow-up evaluations.

2.3 Randomization and Enrollment

This is a single-arm clinical study with no concurrently enrolled control subjects for comparison, and thus randomization is not applicable.

A patient is considered an enrolled subject in the study when the test device enters the patient’s vasculature, also referred to as “test device attempted.” Enrollment of the subject is indicated in the study data system by a response of Yes to Question 1 of the ENRL (Enrollment) CRF, *Was the study device introduced into the anatomy of the subject?*

¹ Although the current version of the study protocol (MD151471 Revision 2) states a maximum of 30 participating sites, approval for 22 sites was granted by FDA in IDE Supplement G160218/S001 dated January 3, 2017.

CONFIDENTIAL INFORMATION

MD133254 Statistical Analysis Plan Template

Revision# 1

Doc Type: GC

3 of 13

2.4 Study Treatment Arms

2.4.1 Test Arm and Test Device

The test arm will consist of consecutively enrolled, prospectively treated and followed subjects who were screened to meet the study eligibility criteria. Test subjects will be treated with the study (test) device: the GORE® CARDIOFORM ASD Occluder.

2.4.2 Control Arm

This is a single-arm clinical study with no concurrently enrolled control subjects for comparison. The comparators for the primary hypothesis tests will consist of performance goals derived from clinical study outcomes for devices indicated for ASD closure.

2.5 Study Endpoints

2.5.1 Primary Endpoints

Co-Primary Endpoint 1: 6-Month Closure Success is defined as a clinical residual defect status of occluded or clinically insignificant as determined by the Echo Core Lab at the 6-month evaluation among subjects with technical success.

Co-Primary Endpoint 2: Composite Clinical Success is evaluated at 6 months after index procedure among subjects with attempted study device closure and is defined as satisfying all of the following criteria:

1. Technical Success: Successful deployment and retention (at conclusion of index procedure) of a GORE® CARDIOFORM ASD Occluder
2. Safety Success:
 - Freedom from any Serious Adverse Event (SAE) related to the device or procedure, as adjudicated by the Independent Data Review Board (IDRB) through 30 days post-procedure
 - Freedom from device events (post-procedure embolization, device removal, or other device reintervention) from completion of the implant procedure through 6 months (180 days) post-procedure
3. Closure Success: A clinical residual defect status of occluded or clinically insignificant as determined by the Echo Core Lab at the 6-month evaluation.

2.5.2 Secondary Endpoints

Technical Success: Successful deployment and retention of the study device at the conclusion of the index procedure

Procedure Success: Technical success and measured residual defect status of occluded, small, or moderate of the target ASD at conclusion of the index procedure

Long-term Closure Success: Closure success evaluated at 12 months and 36 months

Long-term Composite Clinical Success: Composite clinical success evaluated at 12 months and 36 months

CONFIDENTIAL INFORMATION

MD133254 Statistical Analysis Plan Template

[figure not shown]
[figure not shown]
[figure not shown]
Revision#: 1

Doc Type: GC

Safety Outcomes: The proportion of subjects experiencing one or more SAEs within 30 days post-index procedure, and the proportion of subjects experiencing a device event (embolization; device removal; reintervention after completion of index procedure) through 6 months, 12 months, and 36 months post-index procedure

Clinically Significant New Arrhythmia: In subjects without prior history of arrhythmia, any new arrhythmia (documented on ECG) requiring hospitalization, initiation of new long-term medical therapy (persisting > 45 days), or any post-index procedure cardioversion or intervention (pacemaker, ablation, etc.)

2.6 *Statistical Hypotheses*

CONFIDENTIAL INFORMATION

MD133254 Statistical Analysis Plan Template

Revision# 1

Doc Type: GC

2.7 *Sample Size Determination*

2.7.1 [REDACTED]

CONFIDENTIAL INFORMATION

[figure not shown]
MD133254 Statistical Analysis Plan Template

Revision#: 1

Doc Type: GC

A series of six horizontal black bars of varying lengths, each ending in a small white bracket on the right side. The bars are arranged vertically, with the longest bar at the top and the shortest at the bottom. The brackets are positioned at the end of each bar, pointing to the right.

2.7.2

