4.3 Primary Endpoints

4.3.1 Test Method

The co-primary endpoints are both subject-based binomial proportions. For Co-Primary Endpoint 1, 6-Month Closure Success, exact binomial testing at the one-sided 5% significance level will be performed against the performance goal (null hypothesis proportion). If the observed proportion is greater than the performance goal and the statistical test p-value is ≤ 0.05 , then the null hypothesis will be rejected in favor of the alternative hypothesis of acceptable performance. In addition, the 95% one-sided Clopper-Pearson confidence interval lower bound will be reported. Depending on the outcome of this test, Co-Primary Endpoint 2, Composite Clinical Success, will be tested by the same method.

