4.4 Secondary Endpoints

Secondary endpoints (subject-based unless otherwise specified) will be descriptive only; no formal statistical hypotheses will be tested. Secondary endpoints will be summarized at the specified time points using the descriptive statistics described above. No claims of statistical significance will be made based on secondary endpoint results. Any p-values from these tests will not be reported in labeling, but may be used for scientific presentations and manuscripts.

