4.5 Adverse Events

All site-reported AEs will be MedDRA coded and grouped by MedDRA System/Organ Class (SOC) and by MedDRA Preferred Term within SOC. AEs will also be grouped by seriousness (SAE vs. nonserious AE), primary relationship (device, procedure, study medication, and unrelated) and timing of onset (procedure, pre- and postdischarge). AEs will be summarized as rates given by subject-based binomial proportions. The numerator will be the count of subjects who experienced one or more episodes of the AE of interest in the time period of interest. The denominator will be the count of subjects free of the AE of interest through the time period of interest and with sufficient clinical follow-up for the time period of interest, plus the count of subjects in the numerator. Unless otherwise specified for a particular endpoint measure, all enrolled subjects in the analysis set of interest will be considered evaluable and will contribute to the denominator.

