4.6 Baseline Characteristics

Subject demographics, clinical history, risk factors, and pre-procedure defect characteristics will be summarized using descriptive statistics for continuous variables (mean, standard deviation, number of observations, minimum and maximum) and discrete variables (percentage and count/sample).

CONFIDENTIAL INFORMATION

MD133254 Statistical Analysis Plan Template

Revision#: 1

Doc Type: GC

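### Device events through 12 and 36 months are reported as a simple proportion, with no censoring method, no interval and no single stated denominator

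*SAP*

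**What the plan says.** SAP 2.5.2 (Safety Outcomes) defines "the proportion of subjects experiencing a device event (embolization; device removal; reintervention after completion of index procedure) through 6 months" and repeats it for 12 and 36 months. SAP 4.4 says secondary endpoints "will be descriptive only; no formal statistical hypotheses will be tested", and that they are summarized "using the descriptive statistics described above". In the readable text no list of descriptive statistics comes before that sentence. The only list is in SAP 4.6, for baseline data, where the entry is "discrete variables (percentage and count/sample)".

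The one planned interval belongs to the co-primary endpoints: "the 95% one-sided Clopper-Pearson confidence interval lower bound will be reported" (SAP 4.3.1). The worst-case, best-case and tipping-point analyses in SAP 4.9.2 also cover only those endpoints.

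SAP 4.5 (Adverse Events) has a denominator rule in two parts. The first is "The denominator will be the count of subjects free of the AE of interest through the time period of interest and with sufficient clinical follow-up"; anyone with an event is then added. The second is a default, unless specified otherwise for a given measure: "all enrolled subjects in the analysis set of interest will be considered evaluable and will contribute to the denominator". The section does not define sufficient follow-up and does not say whether it applies to the device-event outcome.

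SAP 4.1.3 places post-procedure outcomes in the Technical Success set, and SAP 2.2 follows those subjects to 36 months.

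**The concern.** A risk through 36 months is cumulative, and some subjects may not be observed for the whole period. A simple proportion has two ways to treat someone who leaves event-free at, say, 14 months. It can count that person as event-free to month 36, which pulls the estimate down. Or it can drop that person while keeping anyone who had an event before leaving, which pushes it up. The two sentences of SAP 4.5 correspond to these two choices, so settling the wording alone would only settle the direction of the bias.

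At stake is the interpretation of the long-term embolization, removal and reintervention figure. It would move with retention as well as with device performance. If events are few, a percentage without an interval also invites over-reading, particularly when the count is zero.

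**Working it through.** The documents state no device-event rate, dropout rate or precision target for this endpoint, so there is no plan figure to reproduce. Everything below is conditional on assumptions.

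**Inputs**
- From the SAP: follow-up to day 1095 (3.2), and 125 non-training pivotal subjects (2.2). The size of the Technical Success set is not given; 125 is used as the pivotal maximum.
- Assumed: true 36-month risk p = 3% (range 2-5%); dropout by 36 months d = 5-30%, exponential and independent of events; events either at constant hazard, or 80% at the start and the rest at constant hazard.

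**Formulas, constant hazard**
- le = -ln(1-p) and lc = -ln(1-d)
- Expected observed event fraction: E = le/(le+lc) × [1 - (1-p)(1-d)]
- All-subjects denominator: E
- Follow-up denominator: E / [E + (1-p)(1-d)]

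**Worked case, p = 3%, d = 20%**
- le = 0.0305, lc = 0.2231, (1-p)(1-d) = 0.97 × 0.80 = 0.776
- E = 0.0305/0.2536 × 0.224 = 0.0269, so the all-subjects figure is 2.69% (-0.31 points)
- 0.0269/(0.0269 + 0.776) = 0.0335, so the follow-up figure is 3.35% (+0.35 points)

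With early events, 80% of the risk (2.4%) occurs before any dropout. The formula above then applies to the remaining 97.6% of subjects, with risk 0.6/97.6.

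**Expected estimates when the true risk is 3%**

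| Dropout by 36 months | All subjects, constant hazard | Follow-up rule, constant hazard | All subjects, early events | Follow-up rule, early events |
|---|---|---|---|---|
| 5% | 2.92% | 3.08% | 2.98% | 3.14% |
| 10% | 2.85% | 3.16% | 2.97% | 3.29% |
| 20% | 2.69% | 3.35% | 2.94% | 3.65% |
| 30% | 2.53% | 3.59% | 2.90% | 4.10% |

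At 20% dropout the two denominators differ by 3.35 - 2.69 = 0.66 points (constant hazard) or 3.65 - 2.94 = 0.71 points (early events). Over p = 2-5% and d = 5-30%, the all-subjects figure is 0.5-16% too low in relative terms and the follow-up figure 2.5-37% too high.

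**Kaplan-Meier check.** In 4,000 simulated trials per setting (p = 3%, d = 20%), 1 minus Kaplan-Meier averaged 3.02% (n = 125, constant hazard), 2.97% (n = 125, early events) and 3.00% (n = 460, constant hazard).

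**Sampling error.** The simulated standard deviation of the estimates at n = 125 was about 1.4-1.9 points, larger than the bias. At n = 460, the SAP's non-training maximum, it was about 0.8-1.0 points, and the bias does not shrink with sample size.

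**Precision.** Exact two-sided 95% Clopper-Pearson limits, if all were evaluable: 0/125 gives 0-2.9%; 4/125 (3.2%) gives 0.9-8.0%; 0/460 gives 0-0.8%.

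**The case against.** The strongest reply is that the plan already deals with incomplete follow-up, because SAP 4.5 restricts event-free subjects to those followed long enough. That stands in part: if 4.5 governs device events, the plan is not silent on early leavers. But the same section then makes everyone in the set evaluable by default, and leaves sufficient follow-up undefined. For example, it does not say whether a visit at day 1035, the early edge of the 36-month window (1095 - 60), qualifies.

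Other objections also stand:
- All rates are assumed. With good retention, or with mostly early events and the all-subjects denominator, the bias is trivial.
- At pivotal size, sampling error exceeds the bias.
- The endpoint carries no test or performance goal, and a reader given a count and denominator can work out an exact interval.
- Reading the baseline list in 4.6 as the method for this endpoint is an inference. The pointer in 4.4 has no visible target, so the missing interval is a gap, not a declared choice.
- Kaplan-Meier needs non-informative censoring, and the simulation builds that in.
- Only the protocol summary is available, so a method in the full protocol cannot be excluded.

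A reader might infer that the 36-month device-event risk will be understated, or that the device's long-term safety finding is unreliable. The documents support neither: the direction depends on which denominator is used, and the size depends on rates they do not give.

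**Conclusion.** This holds as a minor, inexpensive improvement. A simple proportion is planned for a cumulative risk over 36 months, with no censoring method, interval or missing-data sensitivity analysis in the readable text. The only denominator rule that might apply contains two versions that err in opposite directions.

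Under an assumed 3% risk and 20% independent dropout, the error is about -0.3 to +0.65 percentage points. At 5% dropout it is within about 0.15 points either way (2.92% to 3.14%). It does not touch the co-primary tests at 6 months, and SAP 4.4 rules out claims of significance from this endpoint. The gain is a long-term figure that depends less on retention and states its own uncertainty.

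**What to change.** In SAP 2.5.2 and 4.4, state the following for device events:
- Estimate the risk at 180, 365 and 1095 days in the Technical Success set as 1 minus Kaplan-Meier, timed from completion of the index procedure and censored at last contact.
- If any deaths occur, use instead the Aalen-Johansen cumulative incidence with death as a competing event. These are two different estimators and should be named separately.
- Give two-sided 95% confidence limits and numbers at risk at each time point.
- Show the crude count beside the estimate with one stated denominator. If that denominator requires sufficient follow-up, define it against the visit windows in SAP 3.2.

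The cost is SAP wording and one extra table, using event and last-contact dates the trial should already hold. No new visits or subjects are needed. The downsides are an assumption of non-informative censoring, and a 36-month figure that may be slightly less favourable than events divided by all implanted subjects.
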